#### **11.4.4.3 Multiplicity considerations**

Statistical significance will be claimed for the primary efficacy endpoint if the computed p-value from the primary analysis is  $\leq 0.05$ . No multiplicity adjustment is considered for secondary efficacy outcomes for this study.

#### **11.4.5 Analyses of safety data**

The summary of safety results will be presented by treatment group. Analysis of safety will be performed using the safety population. Safety data in patients who do not belong to the safety population (eg, exposed but not randomized) will be listed separately, as appropriate.

The safety analysis will be based on the reported AEs and other safety information including clinical laboratory data, vital signs and ECG data. The baseline value is defined as the last available value before the first intake of IMP.

The observation periods for safety during the 96-week double-blind period will be as follows:

- Screening Period is from informed consent to first dose of IMP.
- Treatment-emergent adverse event (TEAE) period is defined as from first dose of IMP up to 4 weeks (28 days) after last dose of IMP or up to inclusion in open label treatment phase, whichever occurs first. The TEAE period can be divided into 2 distinct periods:
  - Treatment Period from first dose of IMP to last dose of IMP,
  - Accelerated elimination period from 1 day after treatment period up to 4 weeks (28 days) after last dose of IMP or up to inclusion in open label treatment phase, whichever occurs first.

- The post-treatment period is from the day after the TEAE period to the end of the 96-week double-blind period, where applicable.

All safety analyses will adhere to sanofi “Guideline for the Analysis and Reporting of Safety Data from Clinical Trials”.

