STUDY DESIGN	
Multicenter, multinational, randomized, double-blind, placebo control, parallel group.
 
The study will consists of:
 
 
A screening period up to 4 weeks.
 
A double-blind treatment period of up to 96 weeks for each patient, including a double-blind period and potentially an open label period.
 
An open-label period including the remainder of the initial 96 weeks, where applicable, and a 96-week extension, ie, up to a maximum of 192 weeks after randomization.
 
An optional additional extension period for young patients with teriflunomide until the patients are 18 years old and/or able to switch to commercial product, whichever comes first.
 
A follow-up period of 4 weeks for patients discontinuing treatment.
 
 
Double-blind treatment period of up to 96 weeks per patient:
 
 
Patients are randomized to either teriflunomide or placebo at 2:1 ratio (110 patients on teriflunomide vs. 55 patients on placebo).
 
Blinded treatment phase begins at randomization and continues to Week 96 or when patient experiences a first relapse or high MRI activity.
 
It includes a blinded PK run-in phase (8 weeks) consisting of 4 weeks with PK sample collection plus 4 weeks of analysis (corresponding to the first 8 weeks after randomization). The PK run-in (8 weeks) phase is intended to provide individual PK parameters to allow the dose adjustment to the 14mg adult-equivalent dose for the rest of the study.
 

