### **4.2 SECONDARY OBJECTIVE(S)**

The secondary objectives of this study are as follows:

- To assess the effect of teriflunomide in comparison to placebo on disease activity/progression measured by brain MRI and on cognitive function.
- To evaluate the safety and tolerability of teriflunomide in comparison to placebo.
- To evaluate the pharmacokinetics (PK) of teriflunomide.

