## 5 STUDY DESIGN

### 5.1 DESCRIPTION OF THE PROTOCOL

EFC11759 is a multicenter, randomized, double-blind, placebo-controlled, parallel-group study. It consists of:

- A screening period up to 4 weeks, designed to evaluate suitability to participate in the trial, in terms of MS diagnosis, MS treatment(s), and safety screening evaluations. No investigational medicinal product (IMP) is administered in this period.
- A double-blind treatment period of up to 96 weeks total duration for each patient
  - Patients are randomized to either teriflunomide or placebo at 2:1 ratio (110 patients on teriflunomide vs. 55 patients on placebo),
  - It includes a blinded PK run-in (8 weeks) phase consisting of 4 weeks of PK sample collection plus 4 weeks of analysis (corresponding to the first 8 weeks after randomization). The PK run-in (8 weeks) phase is intended to provide individual PK parameters to allow the dose adjustment to the 14mg adult-equivalent dose for the rest of the study from Week 8,
  - Patients experiencing a relapse after the PK run-in (8 weeks) and if confirmed by the Relapse Adjudication Panel (RAP) will have the option to continue in an open label period. If RAP does not confirm the relapse, the patient can continue in the double-blind phase or prematurely discontinue the treatment. Similarly, patients with high MRI activity (defined in [Section 8.1](#)) or completing the 96-week double-blind period will have the option to continue in the open label period.
- An open-label period for the remainder of 192 weeks after randomization

The open-label period will follow the double-blind period and last until 192 weeks after randomization. Its duration for a given patient will depend on when the patient enters this period. The duration of the open-label period will be 96 weeks for patients completing the 96-week double-blind period on treatment, and longer for patients switching to open-label during the initial 96 week double-blind period at the occurrence of a confirmed relapse or in case of high MRI activity.

It includes a blinded PK run-in phase (8 weeks, similarly to the double-blind period).

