#### **Adverse events:**

Pre-treatment, treatment-emergent, and post-treatment AEs are defined as AEs that developed or worsened during the screening, TEAE, and post-treatment observation periods. TEAEs will be further differentiated as "TEAEs during treatment period" and "TEAEs during accelerated elimination period".

The analysis will focus on TEAEs. TEAEs during treatment period and TEAEs during accelerated elimination period will be analyzed separately and combined, as applicable. Proportion of patients with at least one TEAE, treatment emergent SAE, TEAE leading to discontinuation, and treatment-emergent AEs of special interest will be tabulated by treatment group. In addition TEAEs will be described according to maximum intensity and relation to the study medication. Non treatment emergent serious AE will be summarized separately.

Adverse event incidence tables will present by system organ class (SOC) (sorted by internationally agreed order), high-level group term (HLGT), high level term (HLT) and preferred term (PT) sorted in alphabetical order for each treatment group, the number (n) and percentage (%) of patients experiencing an AE. Multiple occurrences of the same event in the same patient will be counted only once in the tables within a treatment phase. The denominator for computation of percentages is the safety population within each treatment group.

Patient data listings will be provided for all AEs, TEAEs, SAEs, deaths (if any) and AEs leading to treatment discontinuation.

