#### **Clinical laboratory evaluation:**

The analysis of laboratory data will focus on descriptive statistics and summaries of potentially clinically significant abnormalities (PCSA) and Common Terminology Criteria for Adverse Event (CTCAE) abnormalities based on data from the treatment emergent period. For each parameter, results and changes from baseline will be summarized by treatment group for baseline and each post baseline time point, endpoint, minimum and maximum value. Summary statistics will include number of patients, mean, standard deviation, median, Q1, Q3, minimum and maximum. The proportion of patients who had at least one incidence of PCSA/CTCAE at any time during the TEAE period, treatment period, and accelerated elimination period will be summarized by treatment group. Listings will be provided with flags indicating clinically out-of range values, as well as PCSA values.

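### If teriflunomide delays relapse, the double-blind adverse-event window is shorter on placebo, so crude percentages of steadily accruing events tilt modestly against teriflunomide

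*Protocol*

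**What the plan says.** One of the secondary objectives in Protocol 4.2 is comparative: "To evaluate the safety and tolerability of teriflunomide in comparison to placebo". The double-blind period is the only randomized setting for that comparison; Protocol 11 describes the open-label data as non-controlled.

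Protocol 11.4.5 starts the TEAE period at the first dose and ends it 28 days "after last dose of IMP or up to inclusion in open label treatment phase, whichever occurs first". What brings open-label entry forward is an efficacy outcome. The clinical trial summary puts it this way: "Blinded treatment phase begins at randomization and continues to Week 96 or when patient experiences a first relapse or high MRI activity". Section 5.1 makes entry optional: "Patients experiencing a relapse after the PK run-in (8 weeks) and if confirmed by the Relapse Adjudication Panel (RAP) will have the option to" continue open label, and the same offer goes to patients with high MRI activity.

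The measure is a crude proportion. Under Adverse events the protocol tabulates by arm the "Proportion of patients with at least one TEAE, treatment emergent SAE, TEAE leading to discontinuation" and AESIs, and adds: "The denominator for computation of percentages is the safety population within each treatment group". Laboratory findings follow the same pattern: "The proportion of patients who had at least one incidence of PCSA/CTCAE at any time during the TEAE period". Vital signs and ECG abnormalities are treated likewise.

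Some parts of the protocol do take account of time. First ALT, AST and bilirubin elevations get Kaplan-Meier estimates, liver PCSAs are also shown by duration of exposure, and section 11.4.2 summarizes treatment duration by arm.

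**The concern.** The event that closes the safety window is the event the drug is meant to delay. If teriflunomide works, placebo patients leave the window sooner and have less time in which to record a first adverse event. The denominator still counts every patient once, however long that patient was observed. With identical true adverse-event rates, the tables would show a higher percentage on teriflunomide. A real reduction would be partly hidden, and a small excess could not be separated from longer observation.

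The sponsor adjusts for unequal observation elsewhere. Protocol 11.4.4.2 offsets lesion counts by the number of scans. The open-label SAP (2.4.5.1) restricts interval denominators for AESIs to patients still exposed and event-free. Protocol 11.4.5 states nothing comparable for the randomized adverse-event tables.

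**Working it through.** **Inputs (Protocol 11.1 and 5.1).** 60% of placebo patients relapse by 2 years; hazard ratio 0.5; 20% discontinue in 2 years for reasons other than relapse; maximum double-blind time 96 weeks; relapse-driven switching from Week 8; 110 v 55 patients.

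**Reproducing the plan's figures.**
- Placebo hazard: −ln(0.4)/2 = 0.4581. Teriflunomide: half of that, 0.2291. Two-year rate: 1 − exp(−2 × 0.2291) = 36.8%. All agree.
- Dropout hazard: η = −ln(0.8)/2 = 0.1116 per year.
- Sample size: the probability of an observed relapse in 2 years is λ/(λ+η) × (1 − exp(−2(λ+η))), which is 0.547 on placebo and 0.332 on teriflunomide. N = (1.960 + 0.842)² × (3/0.547 + 1.5/0.332) / (ln 0.5)² ≈ 163, against the stated 165.

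**Mean time in the window.** Let a = 8 weeks = 0.1533 years and T = 96 weeks = 1.8398 years. Only dropout acts before a; dropout and switching act after it.

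Mean = (1 − e^(−ηa))/η + e^(−ηa) × (1 − e^(−(λ+η)(T−a)))/(λ+η)

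- Placebo: 0.1520 + 0.9830 × (1 − 0.3826)/0.5697 = 1.217 years (63.5 weeks)
- Teriflunomide: 0.1520 + 0.9830 × (1 − 0.5630)/0.3406 = 1.413 years (73.7 weeks)
- Ratio: 1.413/1.217 = 1.16

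**Crude percentages at an equal constant adverse-event rate r in both arms.**

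P = r/(η+r) × (1 − e^(−(η+r)a)) + e^(−(η+r)a) × r/(λ+η+r) × (1 − e^(−(λ+η+r)(T−a)))

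For r = 0.3, placebo is 0.0446 + 0.9389 × 0.3449 × 0.7693 = 29.4%. Teriflunomide is 0.0446 + 0.9389 × 0.4683 × 0.6606 = 33.5%.

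| r per year | Placebo | Teriflunomide | Spurious risk ratio |
|---|---|---|---|
| 0.02 | 2.4% | 2.8% | 1.16 |
| 0.3 | 29.4% | 33.5% | 1.14 |
| 0.6 | 48.3% | 54.2% | 1.12 |
| 1.0 | 64.0% | 70.4% | 1.10 |

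**Sensitivity of the 16% excess observation.**
- Switch uptake 80%: 67.3 v 76.1 weeks, 13%. Uptake 50%: 73.7 v 79.9 weeks, 8%.
- True hazard ratio 0.66, 0.8 or 1.0 (full uptake): 11%, 6% or 0%.
- No dropout: 69.3 v 81.0 weeks, 17%.
- To cancel the gap, two-year non-relapse dropout on teriflunomide would have to be about 45%.
- Events confined to the first 24 weeks: crude risk ratio about 1.02.

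**Check on a patient-year alternative.** For steadily accruing events at equal rates, the patient-year rate ratio is 1.00. For events confined to the first 24 weeks at equal hazards, the longer event-free follow-up on teriflunomide dilutes its rate, and the patient-year ratio is about 0.88. That error is in the opposite direction.

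The working ignores adjudication delay, high-MRI switches (the documents give no rate) and the 28-day tail after stopping without a switch, which should be similar in both arms.

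**The case against.** The best counter-argument is that the double-blind analysis has its own SAP, as section 2 of the supplied open-label SAP says. Protocol 11.4.5 also binds safety analyses to a sponsor guideline. Neither was available. A reader might infer that the trial has no time-adjusted harm analysis; the documents do not support that. What stands is narrower: the protocol states this measure and denominator and mentions no exposure adjustment for the double-blind adverse-event tables.

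A reader might also infer that teriflunomide's recognized harms will look inflated. Protocol 3.1.2.2 points the other way: in adults, alopecia arose mostly in the first 6 months, nausea and diarrhea appeared early, and the fall in white cells came in the first 6 weeks. For events of that kind the distortion is about 2%.

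Nor does the window rule itself discard placebo events. Patients who switch from placebo take teriflunomide, so closing the window at open-label entry is right. The problem lies only in comparing crude percentages over unequal windows.

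The tables are descriptive, and the tilt overstates harm rather than hiding it. It is also small against sampling error: at r = 0.3 the 4.1-point gap compares with a 95% half-width of 1.96 × √(0.294 × 0.706/55 + 0.335 × 0.665/110) ≈ 15 points. These facts limit its importance. They do not remove a systematic shift that follows from a stated rule.

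**Conclusion.** The point holds in a qualified form. If teriflunomide delays relapse as assumed, the double-blind crude percentages compare about 63.5 weeks of observation with 73.7. Events that accrue steadily at equal rates of 0.02 to 0.6 per year then show spurious risk ratios of 1.16 down to 1.12, a gap of up to about 6 percentage points.

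This rests on a hazard ratio of 0.5, near-full uptake of an optional switch, equal non-relapse dropout and a constant adverse-event hazard. It shrinks as uptake or efficacy falls and disappears at a hazard ratio of 1. High-MRI switches would widen the gap if commoner on placebo; more stopping for adverse events on teriflunomide would narrow it. Late or steadily accruing harms are the ones affected.

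**What to change.** In Protocol 11.4.5 and the double-blind SAP, unless already there:

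- Keep the crude percentages.
- Beside them, for any TEAE, SAEs, TEAEs leading to discontinuation and AESIs, report Kaplan-Meier or competing-risk cumulative incidence of first event by arm at Weeks 24, 48 and 96, with 95% CIs for the between-arm difference.
- Report first-event rates per 100 patient-years at risk as a supplement. State that they dilute early-clustering events in the arm followed longer, and that censoring at relapse may be informative.
- Interpret crude between-arm differences in late or steadily accruing events alongside these summaries.

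The cost is some analysis-plan wording and a few tables. Adverse-event onset and dosing dates are already collected, and no procedure or treatment rule changes. If the double-blind SAP already contains such an analysis, a cross-reference from the protocol is enough.

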#### **Adverse events:**

Pre-treatment, treatment-emergent, and post-treatment AEs are defined as AEs that developed or worsened during the screening, TEAE, and post-treatment observation periods. TEAEs will be further differentiated as "TEAEs during treatment period" and "TEAEs during accelerated elimination period".

The analysis will focus on TEAEs. TEAEs during treatment period and TEAEs during accelerated elimination period will be analyzed separately and combined, as applicable. Proportion of patients with at least one TEAE, treatment emergent SAE, TEAE leading to discontinuation, and treatment-emergent AEs of special interest will be tabulated by treatment group. In addition TEAEs will be described according to maximum intensity and relation to the study medication. Non treatment emergent serious AE will be summarized separately.

Adverse event incidence tables will present by system organ class (SOC) (sorted by internationally agreed order), high-level group term (HLGT), high level term (HLT) and preferred term (PT) sorted in alphabetical order for each treatment group, the number (n) and percentage (%) of patients experiencing an AE. Multiple occurrences of the same event in the same patient will be counted only once in the tables within a treatment phase. The denominator for computation of percentages is the safety population within each treatment group.

Patient data listings will be provided for all AEs, TEAEs, SAEs, deaths (if any) and AEs leading to treatment discontinuation.

#### **Clinical laboratory evaluation:**

The analysis of laboratory data will focus on descriptive statistics and summaries of potentially clinically significant abnormalities (PCSA) and Common Terminology Criteria for Adverse Event (CTCAE) abnormalities based on data from the treatment emergent period. For each parameter, results and changes from baseline will be summarized by treatment group for baseline and each post baseline time point, endpoint, minimum and maximum value. Summary statistics will include number of patients, mean, standard deviation, median, Q1, Q3, minimum and maximum. The proportion of patients who had at least one incidence of PCSA/CTCAE at any time during the TEAE period, treatment period, and accelerated elimination period will be summarized by treatment group. Listings will be provided with flags indicating clinically out-of range values, as well as PCSA values.

### **Drug-Induced Liver Injury:**

The liver function tests, namely, ALT, AST, alkaline phosphatase and total bilirubin are used to assess possible drug induced liver toxicity. The proportion of patients with PCSA/CTCAE values at any post-baseline visit by baseline status will be displayed by treatment group for each parameter. The proportion of patients with PCSA values at any post baseline visit will also be displayed by duration of exposure for each treatment group.

Time to onset of the initial ALT and AST elevation ( $>3$  x ULN) and total bilirubin elevation ( $>2$  x ULN) will be analyzed for each parameter using Kaplan-Meier estimates, presented by treatment group. A graph of distribution of peak values of ALT versus peak values of total bilirubin will also be presented. Note that the ALT and total bilirubin values are presented on a logarithmic scale. The graph will be divided into 4 quadrants with a vertical line corresponding to 3 x ULN for ALT and a horizontal line corresponding to 2 x ULN for total bilirubin.

The normalization (to  $\leq 1$  ULN) of elevated liver function tests will be summarized by categories of elevation (3 x, 5 x, 10 x, 20 x ULN for ALT and AST, 1.5 x ULN for alkaline phosphatase, and 1.5 x and 2 x ULN for total bilirubin), with the following categories of normalization: never normalized, normalized before permanent discontinuation of study drug, and normalized after permanent discontinuation of study drug. Note that a patient will be counted only under the maximum elevation category.

The incidence of liver related TEAEs will be summarized by treatment group. The selection of preferred terms will be based on standardized MedDRA query (SMQ) Drug related hepatic disorders – comprehensive search (narrow).

### **Vital signs and ECG:**

The analysis of vital signs and ECG will focus on descriptive statistics and summaries of PCSA and outliers based on data from the treatment emergent period. For each parameter, results and changes from baseline will be summarized by treatment group for baseline and each post baseline time point, endpoint, minimum and maximum value. Summary statistics will include number of patients, mean, standard deviation, median, Q1, Q3, minimum and maximum.

The proportion of patients who had at least one incidence of PCSA/outlier at any time during the TEAE period, treatment period, and accelerated elimination period will be summarized by treatment group. Listings will be provided with flags indicating clinically out-of range values, as well as PCSA values.

### **Other safety variables:**

Patients with peripheral neuropathy finding or abdominal ultrasound findings during the treatment emergent period will be summarized by treatment group using counts and percents.

#### **11.4.6 Analyses of pharmacokinetic and pharmacodynamic variables**

Teriflunomide plasma concentrations will be summarized by mean, SD, geometric mean, coefficient of variation, median, minimum, and maximum at each visit where a PK sample is taken for teriflunomide-treated patients.

If date and/or time of the drug intake and/or sampling are missing then the concentration will not be taken into account. Where concentration values are below the lower limit of quantification (LLOQ), one-half of the LLOQ will be used.

Teriflunomide individual post hoc predicted PK parameters ( $C_{max}$  and  $AUC_{0-24}$ ) will be summarized by mean, SD, geometric mean, coefficient of variation, median, minimum, and maximum at each visit of the PK run-in (8 weeks) phase(s) for teriflunomide-treated patients.

Values will be expressed in the tables with no more than three significant figures.

#### **11.4.7 Analyses of quality of life/health economic variables**

Not applicable.

### **11.5 INTERIM ANALYSIS**

No formal interim efficacy analysis of the double-blind treatment period is planned. A Data Monitoring Committee (DMC), independent from the Sponsor and Investigators, will monitor and review all relevant data on a regular basis for the assessment of benefit versus risk and provide recommendations about further continuation of the trial.

## **12 ETHICAL AND REGULATORY STANDARDS**

### **12.1 ETHICAL PRINCIPLES**

This Clinical Trial will be conducted in accordance with the principles laid down by the 18th World Medical Assembly (Helsinki, 1964) and all applicable amendments laid down by the World Medical Assemblies, and the ICH guidelines for Good Clinical Practice (GCP).

In compliance with sanofi public disclosure commitments, this clinical trial will be recorded in the public registry website [clinicaltrials.gov](http://clinicaltrials.gov) before the enrollment of the first patient. The registry will contain basic information about the trial sufficient to inform interested patients (and their healthcare practitioners) how to enroll in the trial.

